8.4.2 Method of Detecting AEs, SAEs, and Other Reportable Safety Events

Care will be taken not to introduce bias when detecting AEs and/or SAEs and other reportable safety events. Open-ended and nonleading verbal questioning of the participant is the preferred method to inquire about AE occurrence.

8.4.3 Follow-up of AE, SAE, and Other Reportable Safety Event Information

After the initial AE/SAE report, the investigator is required to proactively follow each participant at subsequent visits/contacts. All AEs, SAEs, and other reportable safety events including pregnancy and exposure during breastfeeding, cancer, and overdose will be followed until resolution, stabilization, until the event is otherwise explained, or the

participant is lost to follow-up (as defined in Section 7.3). In addition, the investigator will make every attempt to follow all nonserious AEs that occur in randomized participants for outcome. Further information on follow-up procedures is given in Appendix 3.

8.4.4 Regulatory Reporting Requirements for SAE

Prompt notification (within 24 hours) by the investigator to the Sponsor of SAE is essential so that legal obligations and ethical responsibilities towards the safety of participants and the safety of a study intervention under clinical investigation are met.

The Sponsor has a legal responsibility to notify both the local regulatory authority and other regulatory agencies about the safety of a study intervention under clinical investigation. The Sponsor will comply with country-specific regulatory requirements and global laws and regulations relating to safety reporting to regulatory authorities, IRB/IECs, and investigators.

Investigator safety reports must be prepared for suspected unexpected serious adverse reactions (SUSARs) according to local regulatory requirements and Sponsor policy and forwarded to investigators as necessary.

An investigator who receives an investigator safety report describing an SAE or other specific safety information (eg, summary or listing of SAE) from the Sponsor will file it along with the IB and will notify the IRB/IEC, if appropriate according to local requirements.

8.4.5 Pregnancy and Exposure During Breastfeeding

Information in this section is not applicable since participants are infants.

8.4.6 Disease-related Events and/or Disease-related Outcomes Not Qualifying as AEs or SAEs

This is not applicable to this study.

8.4.7 Events of Clinical Interest (ECIs)

There are no events of clinical interest in this study.

8.5 Treatment of Overdose

In this study, an overdose is the administration of more than 1 dose of any individual study vaccine in any 24-hour period.

No specific information is available on the treatment of overdose.

Decisions regarding dose interruptions or modifications will be made by the investigator in consultation with the Sponsor Clinical Director based on the clinical evaluation of the participant.

All reports of overdose must be reported by the investigator within 5 calendar days to the Sponsor either by electronic media or paper. Electronic reporting procedures can be found in the EDC data entry guidelines. Paper reporting procedures can be found in the Investigator Trial File Binder (or equivalent).

8.6 Pharmacokinetics

PK parameters will not be evaluated in this study.

8.7 Pharmacodynamics

Pharmacodynamic parameters will not be evaluated in this study.

8.8 Future Biomedical Research Sample Collection

If the participant's legally acceptable representative signs the future biomedical research consent, the following specimens will be obtained as part of future biomedical research:

- Buccal swab DNA for future research
- Leftover study serum at the central laboratory stored for future research after aliquoting samples for completion of immunogenicity

8.9 Planned Genetic Analysis Sample Collection

Planned genetic analysis samples will not be evaluated in this study.

8.10 Biomarkers

Biomarkers are not evaluated in this study.

8.11 Medical Resource Utilization and Health Economics

Medical Resource Utilization and Health Economics are not evaluated in this study.

8.12 Visit Requirements

Visit requirements are outlined in Section 1.3. Specific procedure-related details are provided in Section 8.

8.12.1 Screening

Screening procedures will be conducted at Visit 1 as outlined in Section 1.3.

8.12.2 Treatment Period/Vaccination Visit

Requirements during the treatment period are outlined in Section 1.3.

If the participant develops a new clinical condition during the study that makes him/her ineligible for the study, the investigator should discuss with the Sponsor Clinical Director as soon as possible. The decision to continue the participant on study intervention requires the mutual agreement of the investigator, the Sponsor, and the participant's legally acceptable representative.

8.12.3 Discontinued Participants Continuing to be Monitored in the Study

A participant may discontinue from study intervention (including receipt of V114 or Pevnar 13™) but continue to participate in protocol-specified, AE-monitoring activities as outlined in Section 1.3, as long as the participant's legally acceptable representative does not withdraw consent. Blood draws for immunogenicity testing in the Premature Infant Immunogenicity Substudy could occur if agreed to by the participant's legally acceptable representative at the discretion of the investigator.

9 STATISTICAL ANALYSIS PLAN

This section outlines the statistical analysis strategy and procedures for the study. Changes to analyses made after the protocol has been finalized, but prior to unblinding, will be documented in a supplemental SAP (sSAP) and referenced in the Clinical Study Report for the study. Post hoc exploratory analyses will be clearly identified in the Clinical Study Report.

9.1 Statistical Analysis Plan Summary

Key elements of the statistical analysis plan are summarized below; the comprehensive plan is provided in Section 9.2 to Section 9.12.

Study Design Overview	A Phase 3, Multicenter, Randomized, Double-blind, Active Comparator-controlled Study to Evaluate the Safety and Tolerability of V114 in Healthy Infants (PNEU-LINK)
Treatment Assignment	Approximately 2400 healthy infants approximately 2 months of age will be enrolled. 
• Full-term infants (gestational age ≥ 37 weeks) will be randomly assigned in a 5:1 ratio to a complete dosing schedule of V114 or Pevnar 13™.• Premature infants (gestational age < 37 weeks) will be randomly assigned in a 1:1 ratio to a complete dosing schedule of V114 or Pevnar 13™.
Analysis Populations	Safety: All Participants as Treated (APaT) Immunogenicity: Per-Protocol (PP) and Full Analysis Set (FAS) population for the Premature Infant Immunogenicity Substudy

Primary Endpoint(s)	
 • Proportion of participants with solicited injection-site AEs (swelling, redness/erythema, tenderness/pain, and hard lump/induration) from Day 1 through Day 14 following any vaccination with V114 or Prevnar 13™ • Proportion of participants with solicited systemic AEs (irritability, drowsiness/somnolence, appetite lost/decreased appetite, and hives or welts/urticaria) from Day 1 through Day 14 following any vaccination with V114 or Prevnar 13™ • Proportion of participants with vaccine-related SAEs from Day 1 through completion of study participation
Key Secondary Endpoints	
Premature Infant Immunogenicity Substudy only:
 
 • Anti-pneumococcal polysaccharide (PnPs) serotype-specific Immunoglobulin G (IgG) Geometric Mean Concentrations (GMCs) for the 15 serotypes contained in V114 at 30 days PD3, prior to Dose 4 and at 30 days PD4 • Anti-PnPs serotype-specific IgG response rates (proportion of participants meeting serotype-specific IgG threshold value of $\geq 0.35 \mu\text{g/mL}$) for the 15 serotypes contained in V114 at 30 days PD3
Statistical Methods for Key Efficacy/Immunogenicity/ Pharmacokinetic Analyses	
Immunogenicity analyses will be conducted for each of the 15 pneumococcal serotypes contained in V114 separately. To address the immunogenicity objectives, evaluation of the IgG GMCs and anti-PnPs serotype-specific IgG response rates will be summarized descriptively.

Statistical Methods for Key Safety Analyses	
P-values (Tier 1 endpoints) and 95% CIs (Tier 1 and Tier 2 endpoints) will be provided for between-vaccination group differences in the percentage of participants with events; these analyses will be performed using the M&N method [Miettinen, O. and Nurminen, M. 1985].

Interim Analyses	
To support the periodic review of safety and tolerability data across the V114 Phase 3 program, an external unblinded statistician will provide unblinded interim safety summaries to an independent DMC for their review. There are no plans to conduct an interim analysis of unblinded immunogenicity data in this study. However, unblinded immunogenicity data will be made available to the DMC upon request to enable a benefit-risk assessment.

Multiplicity	
No multiplicity adjustment is planned.

Sample Size and Power	
Immunogenicity: The immunogenicity objectives for this study are descriptive secondary objectives for the Premature Infant Immunogenicity Substudy only. The study will randomize premature infant participants in a 1:1 ratio to either V114 or Prevnar 13™ vaccination group. The sample size of the Premature Infant Immunogenicity Substudy will be approximately 1% to 2% of overall participants. There is no hypothesis to be evaluated for immunogenicity objectives. Section 9.9.1 provides information about the expected variability of the IgG GMC given the sample size.
 
Safety: Section 9.9.2 provides information about the ability of this study to estimate the incidence of AEs within and between the vaccination groups.

9.2 Responsibility for Analyses/In-house Blinding

The statistical analysis of the data obtained from this study will be the responsibility of the Clinical Biostatistics department of the Sponsor.

This study will be conducted as a double-blind study under in-house blinding procedures. The official, final database will not be unblinded until medical/scientific review has been performed, protocol deviations have been identified, and data have been declared final and complete.

The Clinical Biostatistics department will generate the randomized allocation schedule(s) for study intervention assignment. Randomization will be implemented in an IRT.

Blinding issues related to the planned interim analyses are described in Section 9.7.

9.3 Hypotheses/Estimation

Objectives of the study are stated in Section 3. There is no hypothesis to be evaluated in this study.

9.4 Analysis Endpoints

Safety endpoints for all participants and immunogenicity endpoints for the Premature Infant Immunogenicity Substudy that will be evaluated for within- and/or between-treatment differences are listed below.

9.4.1 Immunogenicity Endpoints

The immunogenicity analyses are for the Premature Infant Immunogenicity Substudy only. A description of immunogenicity assessments for the Premature Infant Immunogenicity Substudy is contained in Section 8.2. Immune responses will be measured for the 15 serotypes contained in V114 (1, 3, 4, 5, 6A, 6B, 7F, 9V, 14, 18C, 19A, 19F, 22F, 23F, and 33F).

The secondary immunogenicity analysis endpoints include:

- Anti- PnPs serotype-specific Immunoglobulin G (IgG) Geometric Mean Concentrations (GMCs) for the 15 serotypes contained in V114 at 30 days PD3, prior to Dose 4 and at 30 days PD4
- Anti-PnPs serotype-specific IgG response rates (proportion of participants meeting serotype-specific IgG threshold value of ≥ 0.35 $\mu\text{g/mL}$) for the 15 serotypes contained in V114 at 30 days PD3

The exploratory immunogenicity analysis endpoint includes:

- Anti-PnPs serotype-specific OPA GMTs for the 15 serotypes contained in V114 at 30 days PD3, prior to Dose 4 and at 30 days PD4

9.4.2 Safety Endpoints

A description of safety measures is contained in Sections 8.3 and 8.4. The analysis of safety results is described in Section 9.6.2.

Safety and tolerability will be assessed by clinical review of all relevant parameters including adverse events and postvaccination temperature measurements following any vaccination with V114 or Prevnar 13™.

The safety analysis endpoints include:

- Proportion of participants with solicited injection-site AEs (swelling, redness/erythema, tenderness/pain, and hard lump/induration) from Day 1 through Day 14 following any vaccination with V114 or Prevnar 13™
- Proportion of participants with solicited systemic AEs (irritability, drowsiness/somnolence, hives or welts/urticaria, and appetite loss/decreased appetite) from Day 1 through Day 14 following any vaccination with V114 or Prevnar 13™
- Proportions of participants with the broad AE categories consisting of any AE, a vaccine-related AE, an SAE, an AE which is both vaccine-related and serious, and discontinuation due to an AE, and the proportion of participants who died
- Participants body temperature measured Day 1 (day of vaccination) through Day 7 following any vaccination with V114 or Prevnar 13™

9.5 Analysis Populations

9.5.1 Immunogenicity Analysis Populations

The immunogenicity analyses will be performed for the Premature Infant Immunogenicity Substudy only. The Per-Protocol (PP) population will serve as the primary population for the analysis of immunogenicity data in this study. The PP population consists of all randomized participants in the Premature Infant Immunogenicity Substudy without deviations from the protocol that may substantially affect the results of the immunogenicity endpoint(s). Potential deviations that may result in the exclusion of a participant from the PP population for all immunogenicity analyses include:

- Failure to receive primary infant series vaccination (V114 or Prevnar 13™ Doses 1, 2, and 3) as per randomization schedule
- Receipt of prohibited medication or prohibited vaccine prior to study vaccination

Additional potential deviations that may result in the exclusion of a participant from the PP population for specific immunogenicity analyses (depending on the time point for analysis) include:

- Failure to receive study vaccine (V114, Prevnar 13™) according to vaccination schedule required at the time point for the analysis
- Failure to receive the scheduled doses of V114 or Prevnar 13™ (at least 28 days between Doses 1 and 2 and between Doses 2 and 3 [for PD3 and pre-dose 4 analysis], 12 months to 1 day prior to 16 months of age for Dose 4 [for PD4 PP analyses])
- Receipt of prohibited medication or prohibited vaccine prior to a blood sample collection
- Collection of blood sample at the time point for the analysis outside of the pre-specified window (as described in Section 1.3)

The final determination on protocol deviations, and thereby the composition of the PP population, will be made prior to the final unblinding of the database. Participants will be included in the vaccination group to which they are randomized for the analysis of immunogenicity data using the PP population.

A supportive analysis using the Full Analysis Set (FAS) population will also be performed for the immunogenicity endpoints. The FAS population consists of all randomized participants who received all study vaccinations required at the time point for the analysis and have serology result. Participants will be included in the vaccination group to which they are randomized for the analysis of immunogenicity data using the FAS population.

9.5.2 Safety Analysis Populations

Safety analyses will be conducted in the All Participants as Treated (APaT) population, which consists of all randomized participants who received at least one dose of study vaccination. Participants will be included in the group corresponding to the study vaccination they actually received for the analysis of safety data using the APaT population. This will be the group to which they are randomized except for participants who take incorrect study vaccination; such participants will be included in the vaccination group corresponding to the study vaccination actually received.

At least 1 temperature measurement obtained subsequent to study intervention is required for inclusion in the analysis of temperature.

9.6 Statistical Methods

Statistical testing and inference for safety and immunogenicity analyses are described in Section 9.6.1 and Section 9.6.2, respectively. Unless otherwise stated, all statistical tests will be conducted at the $\alpha=0.05$ (2-sided) level.

9.6.1 Statistical Methods for Immunogenicity Analyses

This section describes the statistical methods that address the secondary and exploratory objectives about the immunogenicity analyses to be performed for the Premature Infant Immunogenicity Substudy.

For the Premature Infant Immunogenicity Substudy, evaluation of secondary and exploratory endpoints regarding anti-PnPs serotype-specific IgG GMCs and OPA GMTs at 30 days PD3, prior to Dose 4 and at 30 days PD4 for the 15 serotypes contained in the V114 group will be performed within each vaccination group separately. The point estimates will be calculated by exponentiating the estimates of the mean of the natural log values and the confidence intervals (CIs) will be derived by exponentiating the CIs of the mean of the natural log values based on the 1-sample t-distribution. For the secondary endpoints regarding anti-PnPs serotype-specific IgG response rates at 30 days PD3 for the 15 serotypes contained in the V114 group, the within-group CIs will be calculated based on the exact method proposed by Clopper and Pearson [CLOPPER, C. J. and PEARSON, E. S. 1934].

A detailed analysis strategy for immunogenicity endpoints is listed in [Table 3](#).

Table 3 Analysis Strategy for Immunogenicity Variables

Endpoint/Variable (Description, Time Point)	Primary vs. Supportive Approach [†]	Statistical Method	Analysis Population	Missing Data Approach
Anti-PnPs IgG GMCs at 30 days PD3	P	Descriptive Statistics (estimate, 95% CI)	PP	Missing data will not be imputed
	S		FAS	
Anti-PnPs IgG GMCs prior to Dose 4	P	Descriptive Statistics (estimate, 95% CI)	PP	Missing data will not be imputed
	S		FAS	
Anti-PnPs IgG GMCs at 30 days PD4	P	Descriptive Statistics (estimate, 95% CI)	PP	Missing data will not be imputed
	S		FAS	
Proportion of participants with anti-PnPs IgG ≥ 0.35 $\mu\text{g/mL}$ at 30 days PD3	P	Descriptive Statistics (estimate, 95% CI)	PP	Missing data will not be imputed
	S		FAS	
	S		FAS	

[†] P = Primary approach; S = Supportive approach.
^{||} Within group summaries provided using exact method proposed by Clopper and Pearson.
 CI = confidence interval; FAS = Full Analysis Set; GMC = Geometric Mean Concentration;
 IgG = Immunoglobulin G; PD = postdose; PnPs = pneumococcal polysaccharide; PP = Per-Protocol

9.6.2 Statistical Methods for Safety Analyses

Safety and tolerability will be assessed by clinical review of all relevant parameters including AEs and postvaccination temperature measurements.

The analysis of safety results will follow a tiered approach (Table 4). The tiers differ with respect to the analyses that will be performed. Adverse events (specific terms as well as system organ class terms) are either pre-specified as “Tier 1” endpoints, or will be classified as belonging to “Tier 2” or “Tier 3” based on the number of events observed.

Tier 1 Events

Safety parameters or AEs of special interest that are identified constitute “Tier 1” safety endpoints that will be subject to inferential testing for statistical significance with p-values and 95% CIs to be provided for between-treatment differences in the proportion of participants with events; these analyses will be performed using the Miettinen and Nurminen (M&N) method (1985), an unconditional, asymptotic method. However, these p-values and CIs should be regarded as helpful descriptive measures to be used in review, not formal methods for assessing the statistical significance of the between-treatment differences in AEs and safety parameters. For this protocol, solicited injection-site AEs (redness, swelling, hard lump, and tenderness/pain) from Day 1 through Day 14 postvaccination and solicited systemic AEs (irritability, drowsiness, hives or welts, and appetite loss) from Day 1 through Day 14 postvaccination are considered Tier 1 events.

Tier 2 Events

Tier 2 parameters will be assessed via point estimates with 95% CIs provided for differences in the proportion of participants with events (also via the M&N method [1985]) [Miettinen, O. and Nurminen, M. 1985].

Membership in Tier 2 requires that at least 1% of the participants in either treatment group exhibit the event. The threshold of at least 1% was chosen because when less than 1% of participants report AEs in both groups with more events in the V114 group, the 95% CI for the between-group difference in percent incidence will always include zero. Note that when less than 1% of participants report AEs in both groups but with more events in the Prevnar 13™ group or equal in both groups, the 95% CI for the between-group difference may exclude zero. However, the clinical significance of these differences is unknown given the small number of participants who report AEs in this situation (fewer than 4 subjects in each group) and; therefore, these AEs will be categorized as Tier 3 events. Because many 95% CIs for Tier 2 events may be provided without adjustment for multiplicity, the CIs should be regarded as a helpful descriptive measure to be used in review, not a formal method for assessing the statistical significance of the between-group differences in AEs and safety parameters that meet predefined limits of change.

In addition to individual events that occur in at least 1% of participants in any treatment group, the broad AE categories consisting of the proportion of participants with any AE, a vaccine-related AE, an SAE, a vaccine-related SAE, discontinuation due to an AE, and the proportion of participants who died will be considered Tier 2 endpoints.

Tier 3 Events

Safety endpoints that are not Tier 1 or 2 events are considered Tier 3 events. Only point estimates by treatment group are provided for Tier 3 safety parameters.

Table 4 Analysis Strategy for Safety Parameters

Safety Tier	Safety Endpoint [†]	p-Value	95% CI for Between-Group Comparison	Descriptive Statistics
Tier 1	Injection-site redness/erythema (Days 1 to 14)	X	X	X
	Injection-site swelling (Days 1 to 14)	X	X	X
	Injection-site tenderness/pain (Days 1 to 14)	X	X	X
	Injection-site hard lump/induration (Days 1 to 14)	X	X	X
	Irritability (Days 1 to 14)	X	X	X
	Drowsiness/somnolence (Days 1 to 14)	X	X	X
	Hives or welts/urticaria (Days 1 to 14)	X	X	X
	Appetite loss/decreased appetite (Days 1 to 14)	X	X	X
Tier 2	Any AE [†]		X	X
	Any Vaccine-Related AE [†]		X	X
	Any SAE [†]		X	X
	Any Vaccine-Related SAE [†]		X	X
	Discontinuation due to AE [†]		X	X
	Death [†]		X	X
	Maximum temperature measurements meeting the Brighton Collaboration cut points (Days 1 to 7)		X	X
Tier 3	Specific AEs by SOC and PT [‡] (incidence ≥4 of participants in one of the vaccination groups)		X	X
	Specific AEs by SOC and PT [‡] (incidence <4 of participants in all of the vaccination groups)			X

[†] These endpoints are broad adverse event categories. For example, descriptive statistics for the safety endpoint of “Any AE” will provide the number and percentage of participants with at least one AE.
[‡] Includes only those endpoints not pre-specified as Tier 1 or not already pre-specified as Tier 2 endpoints.
 AE = adverse event; CI = confidence interval; PT = preferred term; SAE = serious adverse event; SOC = system organ class; X = results will be provided

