4 STUDY DESIGN

4.1 Overall Design

Approximately 2,400 healthy infants will be randomly assigned to receive V114 (n \approx 2,000) or Prevnar 13™ (n \approx 400) at Visits 1, 2, 3, and 5 (approximately 2, 4, 6, and 12 to 15 months of age, respectively) in the following ratios based on gestational age:

- Full-term infants (gestational age ≥ 37 weeks) 5:1 to V114 or Prevnar 13™
- Premature infants (gestational age < 37 weeks) 1:1 to V114 or Prevnar 13™

It is estimated that approximately 1 to 2% of the overall study population will have a gestational age <37 weeks and will be eligible for inclusion in the Premature Infant Immunogenicity Substudy. There is no prespecified number of premature infants targeted for enrollment in the substudy.

Participants will be followed for local and systemic AEs through Day 14 following each vaccination with V114 or Prevnar 13™. Information for SAEs and deaths, regardless of whether the events are considered to be vaccine-related by the investigator, will be collected from the time consent is signed through completion of participation in the study. An external Data Monitoring Committee (DMC) will conduct a periodic review of safety and tolerability data for the V114 Phase 3 pediatric program. A description of the structure, function, and guidelines for decision making by the DMC, along with the timing and content of the safety reviews will be outlined in the DMC charter. Information regarding the composition of the DMC is provided in Appendix 1.

In addition to the safety assessments, participants in the Premature Infant Immunogenicity Substudy, will also have blood samples for immunogenicity assays drawn at 3 timepoints: (1) 30 days Postdose 3 (PD3), (2) immediately prior to Dose 4, and (3) 30 days Postdose 4 (PD4).

After completion of immunogenicity testing, serum samples will be stored to conduct any additional study-related testing as required by regulatory agencies or the Sponsor. For randomized study participants who provided consent for future biomedical research, leftover sera from the study may be used for the development and/or validation of pneumococcal assays after completion of all study-related immunogenicity testing.

Specific procedures to be performed during the study, as well as their prescribed times and associated visit windows, are outlined in the SoA in Section 1.3. Details of each procedure are provided in Section 8.

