6.3 Measures to Minimize Bias: Randomization and Blinding

6.3.1 Intervention Assignment

Intervention allocation/randomization will occur centrally using an interactive response technology (IRT) system. There are 2 study intervention arms. Full-term infant participants (gestational age ≥ 37 weeks) will be assigned randomly in a 5:1 ratio to receive V114 or Prevnar 13™. Premature infant participants (gestational age < 37 weeks) in the immunogenicity substudy will be assigned randomly in a 1:1 ratio to receive V114 or Prevnar 13™.

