6.3.2 Stratification

Intervention allocation/randomization will be stratified according to the following factors:

- Gestational age < 37 weeks (yes/no)

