3.6 STATISTICAL METHODS

Statistical testing and inference for safety and immunogenicity analyses are described in Section 3.6.1 and Section 3.6.2, respectively. Unless otherwise stated, all statistical tests will be conducted at the $\alpha=0.05$ (2-sided) level.

The correct stratum will be used for analysis regardless of the assigned stratum at randomization (ie, stratification errors will be corrected for the purposes of analysis).

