3.6.2 Statistical Methods for Safety Analyses

Safety and tolerability will be assessed by clinical review of all relevant parameters including AEs and postvaccination temperature measurements.

The analysis of safety results will follow a tiered approach (Table 3). The tiers differ with respect to the analyses that will be performed. Adverse events (specific terms as well as system organ class terms) are either pre-specified as “Tier 1” endpoints, or will be classified as belonging to “Tier 2” or “Tier 3” based on the number of events observed.

Tier 1 Events

Safety parameters or AEs of special interest that are identified constitute “Tier 1” safety endpoints that will be subject to inferential testing for statistical significance with p-values and 95% CIs to be provided for between-treatment differences in the proportion of participants with events; these analyses will be

performed using the Miettinen and Nurminen (M&N) method (1985), an unconditional, asymptotic method. However, these p-values and CIs should be regarded as helpful descriptive measures to be used in review, not formal methods for assessing the statistical significance of the between-treatment differences in AEs and safety parameters. For this protocol, solicited injection-site AEs (redness, swelling, hard lump, and tenderness/pain) from Day 1 through Day 14 postvaccination and solicited systemic AEs (irritability, drowsiness, hives or welts, and appetite loss) from Day 1 through Day 14 postvaccination are considered Tier 1 events.

Tier 2 Events

Tier 2 parameters will be assessed via point estimates with 95% CIs provided for differences in the proportion of participants with events (also via the M&N method [1985]) [Ref. 5.4: 03QCDT].

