3.10 SUBGROUP ANALYSES

An overall summary of AEs and a summary of solicited AEs following any vaccination will be provided for each subgroup (point estimates only) with $\geq 5\%$ of the total number of randomized participants in each vaccination group (except subgroups based on gestational age, which will be provided regardless of the percentage of the total number of randomized participants in each vaccination group).

The following subgroups are planned for evaluation:

- Ethnicity (Hispanic or Latino, Not Hispanic or Latino)
- Race (American Indian or Alaska Native, Asian, Black or African American, Multiple, Native Hawaiian or Other Pacific Islander, White)
- Sex (Female, Male)
- Gestational age < 37 weeks (yes/no)

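### Safety differences use M&N on the pooled population with no stratum named, although allocation is 5:1 in full-term and 1:1 in premature infants

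*Combined protocol and SAP*

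**What the plan says.** Protocol 6.3.1 assigns full-term infants 5:1 to V114 or Prevnar 13. Premature infants, by contrast, "in the immunogenicity substudy will be assigned randomly in a 1:1 ratio to receive V114 or Prevnar 13™". Protocol 6.3.2 states that "Intervention allocation/randomization will be stratified according to the following factors" and lists one factor, gestational age <37 weeks. On numbers, protocol 4.1 says: "It is estimated that approximately 1 to 2% of the overall study population will have a gestational age <37 weeks". It sets no target number and states no upper limit.

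Safety is analysed in the APaT population, "which consists of all randomized participants who received at least one dose of study vaccination" (protocol 9.5.2). The sSAP refines this population in its section 3.5.2 but still pools the two gestational-age strata.

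For Tier 1 events, protocol 9.6.2 says of the between-group differences, CIs and p-values that "these analyses will be performed using the Miettinen and Nurminen (M&N) method (1985), an unconditional, asymptotic method". sSAP 3.6.2 repeats it: "performed using the Miettinen and Nurminen (M&N) method (1985), an unconditional, asymptotic method". Tier 2 differences and CIs use the same method. No stratum or weighting scheme is named in protocol 9.1 or 9.6.2, or in sSAP 3.1 or 3.6.2.

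Two sSAP statements bear on gestational age. Section 3.6 says "The correct stratum will be used for analysis regardless of the assigned stratum at randomization". Section 3.10 lists gestational age as a subgroup, exempt from the 5% size rule, with point estimates only.

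**The concern.** When the allocation ratio differs between strata, the arms differ in composition by design and not by chance. A comparison of crude arm proportions then mixes the vaccine effect with the effect of gestational age. Even with no vaccine effect, the expected crude difference is not zero if risk differs between premature and full-term infants.

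Premature infants are over-represented in the Prevnar 13 arm. An event more frequent in premature infants therefore raises the Prevnar 13 rate, and a real V114 excess is harder to see. An event less frequent in premature infants shifts the difference against V114. With equal risks there is no bias. The documents do not say which case applies to which event.

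The M&N analyses supply the between-group differences and CIs for the primary safety endpoints: the solicited AEs are Tier 1 and vaccine-related SAEs are Tier 2. No adjusted difference or CI is planned beside them.

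**Working it through.** **Inputs from the documents.** About 2,400 infants; 1% to 2% premature, so 24 to 48; allocation 5:1 and 1:1; two-sided 5% level; all randomised infants evaluable for safety (protocol 4.1, 6.3.1, 9.9.2).

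**Assumption, not in the documents.** The risk gap g, defined as premature minus full-term risk.

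1. **The plan's own figure.** Protocol Table 6 gives differences detectable with about 80% probability at 2,000 against 400. A two-proportion power formula with pooled null variance gives 79.1, 79.3, 79.3, 80.1, 80.3, 80.5 and 80.1% for the seven rows. The table reproduces, as an unstratified calculation.

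2. **Arm composition.**
   - 1% premature: the 2,376 full-term infants split 1,980 / 396 and the 24 premature 12 / 12. Arms are 1,992 and 408. Premature share: 12/1,992 = 0.60% against 12/408 = 2.94%, a difference of 2.34 points.
   - 2% premature: 1,960 / 392 and 24 / 24. Arms are 1,984 and 416. Premature share: 24/1,984 = 1.21% against 24/416 = 5.77%, a difference of 4.56 points.

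3. **Bias.** With the same vaccine effect in both strata, expected crude difference = true difference + (premature share in V114 − premature share in Prevnar 13) × g. The size of the second term is:

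| Gap g | 1% premature | 2% premature |
|---|---|---|
| 5 points | 0.12 | 0.23 |
| 10 points | 0.23 | 0.46 |
| 20 points | 0.47 | 0.91 |

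   For g = 10 this equals 0.0023 × 408 ≈ 1 infant, or 0.0046 × 416 ≈ 2 infants, in the Prevnar 13 arm. For comparison, the 95% CI half-width is about 1.6 points at 2% incidence, 3.2 at 10%, and 4.8 to 4.9 at 30% to 70%. A bias of 0.46 is therefore about 29% of the half-width at 2% incidence (0.46/1.6) and about 10% at 30% to 70% (0.46/4.8).

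4. **Effect on the test.** Trials were simulated with the two-sided 5% M&N score test, pooled, and stratified with weights n1·n0/(n1+n0). There were 400,000 trials per detection setting and 200,000 per null setting, except the 2-point-gap rows, which come from a separate run. Premature risk was full-term risk plus g, with the same risk difference in both strata. Entries are the percentage of trials with p<0.05, crude / stratified.

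| Setting | 1% premature | 2% premature |
|---|---|---|
| Table 6 row 4.9% vs 2%, g = 10 | 71 / 79 | 62 / 77 |
| Table 6 row 9.0% vs 5%, g = 10 | 74 / 79 | 69 / 79 |
| Table 6 row 37.3% vs 30%, g = 10 | 78 / 80 | 76 / 81 |
| No effect, 2% full-term, 12% premature | 6.8 / 4.9 | 10.3 / 4.9 |
| No effect, 10% full-term, 20% premature | 5.4 / 5.0 | 6.2 / 5.0 |
| Table 6 row 4.9% vs 2%, g = 2 | 79 / 80 | 78 / 80 |
| No effect, 2% full-term, 4% premature | 5.2 / about 4.9 | 5.4 / about 4.9 |

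   With no gap, the crude test detects the first row in 81% (1% premature) and 82% (2%) of trials. In a separate null simulation the stratified estimate was unbiased to within 0.01 point.

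5. **If more premature infants enrol.** At 5% premature, as an assumption, the shares are 60/1,960 = 3.06% and 60/440 = 13.64%. The bias is then 1.06 points per 10-point gap. At 10% premature it is 1.88.

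**The case against.** **The large figures need a strong assumption.** A 10-point gap at 2% incidence is a six-fold risk in premature infants. With a doubled risk (2% against 4%) the crude test rejects in 5.2% to 5.4% of null trials and loses 1 to 2 points of detection. This stands: the bias is always there when risks differ, but it is often negligible at the planned premature share.

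**The extra null rejections are not spurious harm signals.** At 2% against 12%, nearly all of them point to fewer events on V114. That is correct, but in a study of V114 safety a false signal of fewer V114 events is not a harmless error.

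**Nothing formal rests on these tests.** There is no hypothesis, and the p-values and CIs are labelled descriptive. Protocol section 3 words the primary endpoints as events after V114, and the V114-arm proportions are not biased by the allocation. This limits the consequence, but a descriptive difference can still be biased. Protocol 2.1 also gives the study's purpose as evaluating V114 compared with Prevnar 13.

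**The subgroup summaries show the full-term comparison.** They cover the overall AE summary and all solicited AEs, and the full-term stratum has a single 5:1 ratio. This helps in part. The summaries carry no CI and do not cover temperature or specific AEs.

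**Stratification may already be intended.** The correct-stratum sentence in sSAP 3.6 can be read that way, but no safety method refers to a stratum. On that reading the stratum and weights still have to be written down.

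**Conclusion.** The concern holds. As written, the Tier 1 and Tier 2 between-group differences are biased for any event whose risk differs by gestational age. At the planned 1% to 2% premature share, the bias is 0.23 to 0.46 points per 10 points of risk gap. That is small against most Table 6 differences (1.5 to 7.3 points) and against the CI widths for common solicited AEs. It matters most for uncommon events concentrated in premature infants, or if premature enrolment exceeds the estimate.

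The composition figures follow from the documents. The risk gaps, and all detection and false-signal rates that depend on them, are assumptions. The change should be made because it removes a bias created by the design at almost no cost, not because the expected distortion is large.

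**What to change.** In protocol 9.6.2 and sSAP 3.6.2, state that Tier 1 and Tier 2 differences and 95% CIs, and Tier 1 p-values, use the M&N method stratified by gestational age <37 weeks (yes/no) with Cochran-Mantel-Haenszel weights. Tie the correct-stratum sentence in sSAP 3.6 to this analysis. The supportive analysis of vaccination report card complaints borrows the same methods and should follow. If stratified M&N was already meant, say so and name the weights.

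The cost is a change of wording and a stratum option in the analysis program, with no extra data. In simulation the standard error rises by 0.4% to 1.1% when risks do not differ by gestational age. The premature stratum carries little weight: (12×12/24) = 6 against (1,980×396/2,376) = 330, or 1.8%, at 1% premature; and 12 against 326.7, or 3.5%, at 2%.
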